# 11.9.1 Skeletal Muscle Biopsy

A vastus lateralis muscle biopsy will be performed using a Bergstrom needle in the PBRC Inpatient Unit. After cleansing the skin on the *non-dominant side* of the leg with povidone-iodine solution and placement of a sterile drape, topical anesthesia will be administered using a 50%/50% mixture of bupivacaine 0.5% and lidocaine 2%. The skin will be incised (0.75 cm) with a #11 scalpel. The fascia fibers are separated with the blunt edge of the scalpel and the Bergstrom needle inserted into the *vastus lateralis*. After suction is applied, tissue will be cut and removed. Several passes will be used to obtain up to 500 mg of muscle tissue. Pressure will then be applied and the skin closed with sterile tape. After cleaning the sample, tissue will be processed immediately to develop primary myotubes, while the remaining tissue will be snap frozen in liquid nitrogen and stored for subsequent analyses.

# 11.9.2 Adipose Tissue Biopsy

A subcutaneous abdominal adipose tissue (two-thirds from the umbilicus to the anterior superior iliac spine) will be performed in the PBRC Inpatient Unit. After cleansing the skin on the *non-dominant side* of the abdomen with povidone-iodine solution and placement of a sterile drape, topical anesthesia will be administered using a 50%/50% mixture of bupivacaine 0.5% and lidocaine 2%. The skin will be incised (0.75 cm) with a #11 scalpel. The fascia fibers are separated with the blunt edge of the scalpel and a Bergstrom needle and Mercedes lipoaspirate technique will be applied. After aspiration is applied, ~1.5-2 grams of adipose tissue will be extracted. Pressure will be applied and the skin closed with sterile tape.

# 11.9.3 Tissue biopsy analysis

Tissue samples obtained from the biopsy will be used to address the hypothesis stated in Aim 2 and Aim 3. As shown in **Table 2**, skeletal muscle and adipose tissue samples will be used specifically for: 1) ex-vivo determination of insulin signaling; 2) determination of insulin-stimulated GLUT4 translocation determined by confocal imaging; 3) determination of the prevalence of senescence biomarkers (p16INK4A, γH2AX, phospho-p53, and SA β-gal) and SASP using confocal imaging, Western blot, and mRNA quantification; 4) establishment of primary cultures to measure basal and insulin stimulated glycogen synthesis and lipogenesis using [U-C]glucose; 5) measurement of basal and insulin stimulated glucose uptake using [H]-2-deoxyglucose; and 5) a tissue archive for future analyses. These ex-vivo studies will be performed in [name] and [name] lab.

Table 2:	Table 2: Planned tissue analysis.								
Tissue		Aim 2		Aim 3					
Туре	Total	Primary Culture	Insulin signaling	GLUT4 location	Confocal	RNA	Western blots	Secretome	β-gal staining
SM (mg)	500	150	50	80	25	25	50	-	-
AT (mg)	1500	300	100	200	50	50	100	75	75

SM: Skeletal muscle, AT: adipose tissue.

# **11.10 Compliance procedures**

- Medication reconciliation: Adherence to study drug regimen will be determined by examining the medication possession ratio and the proportion of days covered on a monthly basis. Participants taking study drug ≥80% will be considered compliant.
- PAP adherence: Study participants will be provided with standard PAP therapy. PAP usage will be
  monitored using real-time data acquisition by cloud-based software on a weekly basis during the initial
  weeks and later on a monthly basis. If low compliance is observed, participant will be contacted to
  improve adherence and referred for further PAP adjustment, if needed.

# **12 COMPENSATION**

Participants will receive *up to* \$300 for completion the study (\$100 for Visit 3, \$25 each for Visit 4 and Visit 5, and \$150 for Visit 6/ End-of-Study).

Participants will not be compensated for screening visits. Payment will be received via check requested from the LSU payroll department.

All eligible participants will be provided PAP equipment for the study duration and allowed to keep the equipment for continued OSA treatment after the study is completed. Participants would be advised to followup with a Sleep-board certified physician for clinical care.

# 13 PATIENT SAFETY AND CONFIDENTIALITY

# 13.3 Consent

Consent will be obtained upon screening before initiating study specific procedures. A quiet, comfortable, and private setting for the informed consent process will be provided. The consent process will be explained to the subject, time will be provided to consider all options and when possible, the subject will be provided a copy of the consent form well in advance for review at home. Study staff will consider the subject's likely reading abilities and provide an impartial witness in the informed consent process if necessary. All questions will be answered. Coercion or other undue influences will be avoided through the use of a quiet, comfortable, and private setting will be used for the informed consent process. The subject will be told that informed consent can be revisited at any time and consent can be withdrawn at any time without affecting the subject's medical care. The informed consent process will continue throughout the subject's participation in the study and consent will be informally verified on a continuing basis. Significant new information will be given to the subject as it is available.

# 13.4 Risks to Participants

This Human Subjects Research meets the definition of a Clinical Trial. This study does not involve major risk to participants. Efforts to minimize the potential risks of the assessment methods and outcome variables include frequent monitoring by the investigators to assure that no volunteer suffers any adverse effects from participating in the research.

The known risks, inconveniences, or side effects from the proposed procedures in the project are included here (in alphabetical order):

Potential Risks and Efforts to Minimize the Risks					
Procedure	Potential Risks	Efforts to Minimize the Risks			
Adipose Tissue Biopsies	Pain, infection, scaring, bleeding, and loss of sensation to the skin (usually temporary but in some cases permanent) around biopsy sites are possible risks.	Trained nurses and personnel will be performing the biopsies using sterile technique after local anesthesia to minimize risks.			
Ambulatory Blood Pressure Monitoring	There are no known risks associated with the blood pressure monitor. Some discomfort having the cuff inflate every 30 minutes around the clock may be experienced.	should the subject become			
Blood Draws	Bruising, bleeding, pain, and infection pose minimal risks.	Trained phlebotomists and personnel will use sterile technique.			

Confidentiality of Data	Taking part in this research may involve providing information that one considers confidential or private. There is a slight risk that data could be revealed inappropriately or accidentally	Study researchers and staff will take steps to protect data that is collected. Efforts, such as coding research records, keeping research records secure and allowing only authorized people to access research records, will be made to keep the data safe.
		The amount of radiation used for this procedure is very small. The radiation dose for a DXA scan is equivalent to the radiation an individual is naturally exposed to in the environment in less than one day. Scans will not be performed on any subject who is pregnant. A pregnancy test will be performed within 72 hours before the scan on females of child-bearing- potential.
Dual-Energy X- Ray Absorptiometry (DXA)	DXA measures the amount of bone, muscle, and fat in the body. The expected dose of radiation is minimal, equivalent to less than 0.0004mSv or ~12 h of exposure to the sun.	Lifetime radiation exposure: We are exposed to radiation in the environment on a daily basis; however, some scientists have suggested that humans have a lifetime maximum exposure limit. Exposure to radiation is not without risk, but it is difficult to quantify the exact amount someone is exposed to. By participating in this study, individuals will be exposed to radiation that will add to this lifetime maximum exposure limit. If participants believe that they have been exposed to a significant amount of radiation as part of your occupation or due to treatment for a specific medical condition, they would be asked to notify the study team to discuss whether this study would be appropriate for them.
Fasting for 10-h	Nausea.	Light snacks will be available to eat once fasting procedures completed.

Oral Glucose Tolerance Test (OGTT)	There is a possibility of pain, bruising, or infection at the site of the needle insertion for the IV line. The drink may cause nausea, vomiting, abdominal bloating or a headache.	Trained nurses and personnel minimize the risk associated with IV. Participant may choose to drink the glucose solution more slowly or stop drinking completely.		
Oximetry	There are no significant risks related to overnight use of oximeter other than temporary discomfort while wearing the device.	The device can easily be removed should the subject become uncomfortable.		
Questionnaires	Uncomfortable answering questions.	Participants may skip any questions.		
Skeletal Muscle Biopsies	Pain, infection, scaring, bleeding, and loss of sensation to the skin (usually temporary but in some cases permanent) around biopsy sites are possible risks.	Trained nurses and personnel will be performing the biopsies using sterile technique after local anesthesia to minimize risks.		
Sleep Study	There are no significant risks related to sleep study (polysomnography). However, to obtain the polysomnographic measurements, it may be necessary to glue many small surface electrodes on the participant's scalp and face. The adhesive used to attach these wires has a strong smell, and the subject may feel a scratching sensation when the wires are applied.	Trained personnel will place the electrodes using adhesives approved for sensitive skin.		

In addition to the risks listed above, participants may experience a previously unknown risk or side effect.

# 13.5 Safety Monitoring

# 13.5.1 Personnel responsible for the safety review and its frequency

The Principal Investigator ([name], PI) and the Medical Investigator ([name], MI) will be responsible for monitoring the data, assuring protocol compliance and conducting the safety reviews on a quarterly basis (including at the time of continuing review). During the review process, the Principal Investigator will evaluate whether the study should continue unchanged, requires modification/amendment or should close to enrollment. Findings will be reported at the time of continuing review. The IRB, PI or regulatory body (e.g., FDA, OHRP) has the authority to stop or suspend the study or require modifications.

#### 13.5.2 Determination of study risk

The risks associated with the current study are deemed moderate for the following reasons:

- We do not view the risks associated with the study procedures including metformin use, fat biopsy and muscle biopsy as minimal.
- Given the established safety and validity of metformin and biopsy procedures in our prior work, we do not view the proposed study as high-risk.

Although we have assessed the proposed study as one of moderate risk, the potential exists for anticipated and/or unanticipated adverse events, serious or otherwise, to occur since it is not possible to

predict with certainty the absolute risk in any given individual or in advance of firsthand experience with the proposed study methods. Therefore, we provide a plan for monitoring the data and safety of the proposed study as follows:

### 13.5.2.1 Adverse events

In this study, an **adverse event or experience** is defined as any health-related unfavorable or unintended medical occurrence that happens throughout study participation. Examples of adverse events include but are not limited to the following:

- A clinically significant laboratory or clinical test result.
- An event that results in missing a study visit.
- An event that requires a visit to a physician.
- An event that occurs as a result of a study procedure.
- Unanticipated or untoward medical events that may be study related.

# 13.5.2.2 Attribution of adverse events

Adverse events for each subject participating in the study will be monitored and attributed to the study procedures/design by the Principal Investigator (PI) ([name]) and/or Medical Investigator (MI) ([name]) according to the following categories:

- Definite: Adverse event is clearly related to investigational procedure(s)/agent(s).
- Probable: Adverse event is likely related to investigational procedure(s)/agent(s).
- Possible: Adverse event may be related to investigational procedure(s)/agent(s).
- Unlikely: Adverse event is likely not related to the investigational procedure(s)/agent(s).
- Unrelated: Adverse event is clearly not related to investigational procedure(s)/agent(s).

# 13.5.2.3 Plan for grading adverse events

The following scale will be used in grading the severity of adverse events noted during the study:

- Mild adverse event
- Moderate adverse event
- Severe or medically significant

# 13.5.2.4 Plan for determining seriousness of adverse events

In addition to grading the adverse event, the PI and MI will determine whether the adverse event meets the criteria for a Serious Adverse Event (SAE). An adverse event is considered serious if ANY of the following apply:

- It is life-threatening.
- It results in inpatient hospitalization or prolongation of existing hospitalization.
- It results in persistent or significant disability or incapacity.

- It results in a congenital anomaly or birth defect.
- It results in death.

• Based upon appropriate medical judgment, it may jeopardize the subject's health and may require medical or surgical intervention to prevent one of the other outcomes listed in this definition.

• It adversely affects the risk/benefit ratio of the study.

An adverse event may be graded as severe but still not meet the criteria for a SAE. Similarly, an adverse event may be graded as moderate but still meet the criteria for an SAE. It is important for the PI to consider the grade of the event as well as its seriousness when determining whether reporting to the IRB is necessary.

#### 13.5.2.5 Plan for reporting adverse events

#### • Reporting adverse events to the IRB

The investigator will report the following types of adverse events to the IRB:

- o Serious AND unanticipated AND possibly, probably or definitely related events.
- o Anticipated adverse events occurring with a greater frequency than expected.
- o Other unanticipated problems involving risks to participants or others.

These adverse events or unanticipated problems involving risks to participants or others will be reported to the IRB within 10 working days of becoming known to the investigator, using the appropriate forms found in IRB Manager.

#### Reporting adverse events to co-investigators

The following individuals and funding and/or regulatory agencies will be notified of adverse events:

- All co-investigators listed on the protocol.
- Study sponsor(s) Pennington NORC.
- National Institutes of Health.

The Principal Investigator ([name]) and/or Medical Investigator (MI) ([name]) will conduct a review of all adverse events upon completion of every study subject. The Principal Investigator will evaluate the frequency and severity of the adverse events and determine if modifications to the protocol or consent form are required.

#### 13.5.2.6 Surveillance Procedures

Adverse events will be documented during the scheduled visits or during phone calls during offweeks. For each sign, symptom or adverse event, the following information will be recorded:

- A brief descriptor of the adverse event
- Start and stop dates
- Intensity (mild / moderate / severe)
- Whether the AE was "serious" or not (as defined below)

- Causal association with the intervention assigned (unrelated/ unlikely/ possible/ probable/ definite)
- Outcome (resolved / resolved with sequelae / improving / still present and unchanged / death)
- Action taken with respect to the intervention (none / intervention temporarily discontinued / medical therapy required / intervention permanently discontinued / other).

Adverse event data will be collected from the date of consent until the final visit. Adverse event data will be analyzed quarterly, but serious or life-threatening adverse events may require immediate reporting and follow-up. We anticipate most adverse events will be mild and the subject will be able to resume activities within a day or two of reporting the event.

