### 7. ASSESSMENT SCHEDULE AND PROCEDURES

An overview of all clinic visits and assessments is presented in **Table 1**. Eligibility of the study participants will be determined during two screening visits. Study procedures will require 4 visits. Among the study visits, Visit 3 and Visit 6 will last ~ 4.5 h each during which baseline and 3-month follow-up measures will be obtained. Visit 4 and Visit 5 will comprise of short (~ 45 min) visits during which compliance to study drug and PAP would be monitored and study drug will be dispensed.

Table 1: Clinic Visits and Asses		1				
	Screening	Screening Visit 2	Test Period			
Assessment	Visit 1		Visit 3 Baseline	Visit 4 Month 1	Visit 5 Month 2	Visit 6 Month 3
Informed consent	Х					
Inclusion/exclusion criteria	Х					
Medical History (Health Questionnaire)	X					
Physical examination	Х					
Concomitant medications	Х					
Vital Signs (BP, pulse)	Х					
Body weight	Х		Х			X
Height and BMI	Х					
Oximetry	X					
Blood draw (fasting)	X		Х			X
Overnight Sleep study		Х				
Waist, hip, neck, circumference			Х			X
OGTT			Х			X
Urine Pregnancy testing*			Х			X
Questionnaires			Х			X
Dietary assessment (food record)			Х			X
Whole body DXA			Х			X
Abdominal fat biopsy			Х			X
Muscle biopsy			Х			X
ABPM -24 hour			Х			X
PAP provided			Х			
Randomization			Х			
Drug Dispense			Х	X	X	

#PBRC 2020-033

Adverse events		Х	Х	Х
Monitoring adherence		Х	Х	Х
(PAP and Drug)				

\*urine pregnancy testing is only for women of childbearing potential. BP: blood pressure; BMI: body mass index, OGTT: oral glucose tolerance test; DXA: dual energy X-ray absorptiometry; ABPM: ambulatory blood pressure monitoring; PAP: positive airway pressure.

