### 10.2 Visit 4 (Month 1) and Visit 5 (Month 2)

During this visit, participants will be asked to bring remaining study drug to determine compliance. Participants will also be questioned for any possible side-effects and adverse events.

Non-compliant participants (<80% drug taken as determined by pill count) will be interviewed to determine factors that resulted in poor compliance. If needed, guidance will be provided to improve management of minor side-effects which may improve adherence such as bloating etc. Patients will continue in the study but will be counselled on the importance of taking their medication as prescribed by the study protocol.

Compliance to PAP therapy for OSA will also be monitored through cloud-based technology. Non-compliant participants (using PAP <4hours each night) will be interviewed to determine factors resulting in poor adherence. If needed, participants may be referred to consulting DME (ApneaMed) /physician ([name]) to help improve CPAP adherence.

All participants will be reminded to continue /improve adherence for both PAP and study drug.

Study drug for the next ~30 days will be dispensed.

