#### 10.3 Visit 6 (Month 3/ End-of-Study)

All procedures from Visit 3 will be repeated and any remaining study drug will be collected and disposed. Additionally, information related to potential adverse events will also be collected.

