# **11.9 Biopsies**

On the mornings of Visit 3 and Visit 6, skeletal muscle and adipose tissue biopsies will be performed in the PBRC Inpatient Unit on the *non-dominant* side of the body.

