# 13.6 Withdrawal of Participants

There is no risk associated with withdrawal from the study. Participants may be withdrawn from the study if either the PI or MI feels that their continued participation would jeopardize the participant's health. In case of withdrawal, early termination procedures would be followed including documentation of adverse events, drug side effects, and reason for withdrawal. Any remaining study drug would also be collected at this time.

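### Adverse-event collection closes at Visit 6, the day both biopsies are repeated, and no later enquiry is planned in the available protocol text or Table 1

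*Combined protocol and SAP*

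**What the plan says.** Section 13.5.2.6 sets the window for safety data: "Adverse event data will be collected from the date of consent until the final visit". The same section has events recorded at scheduled visits or in telephone calls in the weeks between them. It does not give the number of calls.

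Section 10.3 is headed as the Month 3 and end-of-study visit and says: "All procedures from Visit 3 will be repeated and any remaining study drug will be collected and disposed". It then adds: "Additionally, information related to potential adverse events will also be collected". Section 11.9 confirms the timing of the tissue sampling: "On the mornings of Visit 3 and Visit 6, skeletal muscle and adipose tissue biopsies will be performed". Section 7 says "Study procedures will require 4 visits", numbered Visits 3 to 6, and Table 1 has no column after Visit 6.

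For the two intermediate visits, section 10.2 provides: "Participants will also be questioned for any possible side-effects and adverse events". For people who leave early, section 13.6 provides: "In case of withdrawal, early termination procedures would be followed including documentation of adverse events, drug side effects, and reason for withdrawal".

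The risk table in section 13.4 says of each biopsy: "Pain, infection, scaring, bleeding, and loss of sensation to the skin (usually temporary but in some cases permanent) around biopsy sites are possible risks".

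**The concern.** The last invasive procedures fall on the day the collection window closes. Some of the complications that section 13.4 lists need not be apparent within hours: an infection may develop later, and temporary loss of sensation cannot be told from permanent loss on the day. A procedure-related event counts as an adverse event under section 13.5.2.1. Yet a new, non-serious one that appears after a completer goes home from Visit 6 meets no planned question.

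What is at stake is the completeness of the safety record. Sections 13.5.2.5 and 13.7 have the investigators alert the IRB when events are more frequent than expected, and late biopsy complications could be undercounted in that comparison. Section 13.5.2 does not regard the biopsy risk as minimal. It also does not regard the study as high-risk, and section 13.5.2.6 expects most events to be mild, so the stakes are modest. The Matsuda Index analysis is not touched.

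**Working it through.** The plan gives no figure to reproduce here. The check compares the sections and then counts.

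**Contacts planned after each biopsy day (completers)**

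| | Visit 3 biopsies | Visit 6 biopsies |
|---|---|---|
| Later scheduled visits with an adverse-event enquiry | 3 (Visits 4, 5 and 6; sections 10.2 and 10.3) | 0 |
| Calls between visits (section 13.5.2.6) | Possible, number not given | None scheduled; the window has closed |
| Next scheduled visit | About 1 month later | None |
| Enquiry on the biopsy day itself | No Visit 3 mark in Table 1 as read below | Yes (section 10.3), order relative to the biopsies not stated |

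Section 7 gives Visit 6 a length of about 4.5 hours, so planned observation after the last biopsies is at most that long. The adverse-event row of Table 1 is broken in the text available. Its three marks are read as Visits 4, 5 and 6, which agrees with sections 10.2 and 10.3.

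**Size**

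Inputs: enrolment of at most 20 (section 5.1); two tissues, each sampled at two visits (section 11.9); completers, C. It is assumed that all 20 have both baseline biopsies and that only completers have the Visit 6 biopsies.

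- Visit 6 biopsies = 2 × C.
- All biopsies = 2 × 20 + 2 × C.
- Share without a later planned enquiry = 2C / (40 + 2C).

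Results:

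- C = 20: 40 / 80 = 50%.
- C = 18 (the ceiling on completers mentioned in section 14.4.1): 36 / 76 = 47.4%.
- C = 15 (an assumption, for illustration): 30 / 70 = 42.9%.

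The share rises with C, so 50% is the maximum. Both tissues are taken from the same person on the same morning and an enquiry is made per person. The natural unit is therefore the participant: at most 20 people lack one later contact.

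The documents give no biopsy complication rate, so the expected number of missed events cannot be calculated.

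**The case against.** The strongest case on the other side has four parts.

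1. **The window may not shut at discharge.** Section 13.5.2.1 ties adverse events to study participation and counts clinically significant test results among them. The 24-hour blood pressure recording starts on the afternoon of Visit 6 and may be repeated (section 11.8). Three non-consecutive diet days (section 11.6) span at least five days. Section 13.4 also promises frequent monitoring by the investigators. This shows that some recording could run past Visit 6, but none of these sections attaches a question about the biopsy sites. It softens the gap without closing it.

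2. **Other safety provisions exist.** There are quarterly reviews (section 13.5.1), a review as each participant completes and IRB reporting (section 13.5.2.5), and follow-up wording for serious or life-threatening events (section 13.5.2.6). The reviews and reports work on events already known to the investigators. The wording on serious events stands, so the point is confined to non-serious ones. People who withdraw are covered by section 13.6.

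3. **The consent pages were not available.** They may tell participants to report late problems. A reader might infer that late complications would come to light only if volunteered; the visible text does not allow anything so firm. It supports only that no enquiry is planned in the text available.

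4. **Late complications can still be described from the baseline biopsies.** Up to 40 of these have later enquiry. That is true and reduces what is lost, but it does not record what happens to the individual after Visit 6.

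**Conclusion.** The point holds in a limited form. Applied as written, the collection rule leaves new, non-serious, delayed complications of the Visit 6 biopsies without planned capture in up to 20 completers (at most 40 of 80 biopsies). It rests on the available protocol text and Table 1, and on the reading of the broken table row given above. It is a cheap improvement to consider, with medium confidence because the consent pages could not be read.

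Three stronger readings are not supported:

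- That half of all complications would be missed. The 50% is a share of procedures, follows from having two biopsy days, and is a maximum.
- That 18 to 20 completers, or 47% to 50%, is a range. Sections 5.1 and 14.4.1 both state ceilings, and section 14.4.1 speaks of detectability and does not forecast retention.
- That the plan has no way to close an unresolved event. The outcome categories in section 13.5.2.6 already include one for events still present, so following open events to resolution is a separate preference and not part of this point.

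**What to change.** In section 13.5.2.6, extend the collection window to one telephone contact after Visit 6, at an interval set by the investigators, with a question about new problems including the biopsy sites. The section already uses telephone calls, so no new method is needed. Add the contact to Table 1.

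The cost is one short call per completer (at most 20 calls), one added contact in Table 1 and a small amendment. Participation becomes slightly longer, so the chosen interval should be checked against the four-month limit in section 3.
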